#### 7 STUDY DESIGN, ENROLLMENT, AND DURATION

#### 7.1 Study Design

This is a retrospective-prospective study design. Patients who completed treatment approximately 3 years (range of 2-4 years) at time of IRB approval of this study will be identified and any existing data in the patient's record will be collected in addition to conducting office visits for long-term follow-up.

The study will include:

Identifying patients, retrospectively, who completed treatment a minimum of 2 years prior to study onset. The history, demographic and treatment data will be collected from up to 320 subjects previously treated with eBx for the treatment of NMSC and up to 320 subjects previously treated with Mohs surgery for the treatment of NMSC. Data will be collected from enough patients to achieve the required sample size of 293 lesions in each treatment group. Patients will then return for long-term follow-up visit for the investigators to assess the lesion site, document absence of recurrence, chronic toxicities, and collect patient reported outcomes.

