#### 7.5 Secondary Endpoints

- i. Comparison of long-term toxicities related to eBx vs. Mohs treatment;
- ii. Comparison of long-term cosmetic outcomes for lesions treated for NMSC with eBx vs. Mohs;
- iii. Chronic toxicities;
- iv. Patient Survey for reporting Patient Reported Outcomes (PRO)

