#### 7.6 Eligibility Criteria

#### 7.6.1 Inclusion Criteria

All answers must be YES to have lesions included in this study.

- 1. Previously completed treatment for non-melanoma skin cancer using Xoft eBx Electronic Brachytherapy System or Mohs surgery;
- 2. Provides informed Consent;
- 3. Greater than 40 years of age;
- 4. Pathological diagnosis confirmed to be squamous cell or basal cell carcinoma prior to treatment;
- 5. Cancer Staging included in this study:
  - Stage 0: Tis, N0, M0
  - Stage 1: T1, N0, M0
  - Stage 2: T2, N0, M0 and  $\leq$  4cm in diameter

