#### 8.1.1 Step by Step Instructions

1. The eBx patients will be determined first. They are called consecutively based on the length of follow-up required by this protocol.

2. As patients are called back for consenting and follow-up visits begin, the patients treated with Mohs are called consecutively and asked to come back who match those treated with eBx.

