#### 8.2 Long-term Follow-up Visits

Each patient agreeable to participating in this study will be asked to return for an office visit for prospective data collection. There may be up to two (2) visits over the next years.

Since the subjects have already received treatment, the study cannot include a randomization design. Each lesion from the eBx treatment group will be matched to a lesion treated with Mohs surgery. The variables used for matching will be:

- Calendar year of treatment for equivalent follow-up
- Patient age bracket [Attempt to ensure 15-year brackets or less]
- Lesion diagnosis (BCC or SCC)
- Lesion size range (< 1 cm,  $\geq$ 1 and <2 cm,  $\geq$ 2 cm and <3 cm,  $\geq$ 3 and  $\leq$ 4 cm)
- Lesion Location

It is not expected that there will be an equal number of patients treated with eBx and Mohs at each site, as some practices may not use both types of treatment modalities. To ensure that a minimum of 293 lesions are matched, the participating sites will be asked for a list of all patients treated approximately 2 to 4 years prior to study onset including the variables being used for matching. The study sponsor will then compare all the available data from the participating sites and notify each site which patient and lesion data will be included in the study.

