#### Table 1. Case Report Forms

#### **12.2 Statistical Analyses**

This is a multi-center, retrospective-prospective study comparing non-melanoma skin cancer treatment (basal cell carcinoma and squamous cell carcinoma) using Xoft electronic brachytherapy (eBx) results compared to a Mohs micrographic surgery. The lesion data will be matched on 4 categories as outlined in Section 8 and the results will be compared between the two treatment groups.

A sample size calculation comparing treatment of NMSC with eBx to treatment with Mohs micrographic surgery was done using a 1.5% historical 3-year recurrence rate for NMSC treated with Mohs, and a 2.5% non-inferiority margin. A total of 293 lesions for each treatment group will provide 80% power with a 0.05 alpha level of significance. Data from up to three hundred-twenty (320) subjects with each type of treatment will be collected to ensure a sufficient number of lesions to adequately power the study. There may be more than one lesion per patient that is matched to another lesion in the other treatment group. The total lesions will be compared in this study and the lesion count determines the number of patients that are ultimately enrolled.

The primary endpoint of freedom from recurrence and the secondary endpoints will be summarized for each treatment group and Chi-square tests performed as applicable. All tests will be 2-sided, with significance level set at 0.05, and performed using SAS (version 9.4 SAS Institute, Inc., Cary, NC).

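### Section 12.2 tests total lesions with Chi-square tests and names no method for matched pairs or for several lesions per patient; the net direction of the resulting error is not known

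*Combined protocol and SAP*

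**What the plan says.** Three features of the plan meet here.

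- **Matching.** The study name in the synopsis describes a matched-pairs cohort. Section 8.2 states: "Each lesion from the eBx treatment group will be matched to a lesion treated with Mohs surgery". Section 8.1.1 recruits on that basis: "the patients treated with Mohs are called consecutively and asked to come back who match those treated with eBx".
- **Several lesions per patient.** Section 12.2 allows it: "There may be more than one lesion per patient that is matched to another lesion in the other treatment group". Eligibility is judged by lesion (7.6.1: "All answers must be YES to have lesions included in this study"), and the size target is in lesions (7.1: "Data will be collected from enough patients to achieve the required sample size of 293 lesions in each treatment group").
- **Analysis.** Section 12.2 says "The total lesions will be compared in this study and the lesion count determines the number of patients that are ultimately enrolled", and then "The primary endpoint of freedom from recurrence and the secondary endpoints will be summarized for each treatment group and Chi-square tests performed as applicable". Tests are two-sided at 0.05.

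The protocol names no McNemar or other paired test, conditional model, GEE, mixed model, robust variance or design effect. No separate SAP is included.

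**The concern.** A Chi-square test on two lesion counts treats all 586 lesions as independent. The design creates two kinds of dependence that can break this.

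- **Same patient, same group.** Lesions on one patient share skin, sun exposure, operator and follow-up. If their outcomes are positively correlated, the usual standard error is too small and the test too liberal.
- **Matched pair.** Paired lesions share treatment year, age bracket, histology, size band and site. If their outcomes are positively correlated, the usual standard error of the difference is too large and the test conservative. Positive correlation between lesions of one patient in opposite groups would act the same way.

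At stake are the error rate and power for recurrence, where few events are expected, and the same quantities for lesion-level secondary endpoints such as the cosmetic comparison (7.5: "Comparison of long-term cosmetic outcomes for lesions treated for NMSC with eBx vs. Mohs").

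**Working it through.** **Inputs from section 12.2.** Mohs recurrence 1.5%; margin 2.5 percentage points (absolute scale assumed, since it reproduces the plan's figure); 293 lesions per group; 80% power; alpha 0.05. The documents give no lesions-per-patient distribution, within-patient correlation (ICC) or pair correlation (rho). All values of these below are assumptions.

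**1. The plan's own figure.** For independent lesions and a true difference of zero:

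n = (1.645 + 0.842)² × 2 × 0.015 × 0.985 / 0.025² = 292.3, which rounds up to 293.

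Power at 293 = Φ(0.025 / √(0.02955/293) − 1.645) = Φ(2.489 − 1.645) = 80.1%.

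So 293 reproduces at one-sided 0.05 with no correlation of either kind. This is the simplest reading but not the only one: at one-sided 0.025 the formula gives 371.1, and a variance factor of 0.79 would also bring that to 293.

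**2. Variance factor.** VF = 1 + (m_w − 1) × ICC − rho, where m_w = Σm²/Σm is the size-weighted mean number of lesions per patient. Then:

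- lesions needed per group = 292.3 × VF
- power at 293 = Φ(2.489/√VF − 1.645)
- risk of false non-inferiority if the dependence is ignored = Φ(−1.645/√VF)

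**3. Clustering only (rho = 0), each patient having 1 or 2 lesions.**

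| Mean lesions | m_w | ICC | VF | Power at 293 | Lesions per group for 80% | False non-inferiority if ignored |
|---|---|---|---|---|---|---|
| 1.2 | 1.6/1.2 = 1.333 | 0.1 | 1.033 | 78.9% | 302 | 5.3% |
| 1.5 | 2.5/1.5 = 1.667 | 0.3 | 1.20 | 73.5% | 351 | 6.7% |
| 2 | 2 | 0.3 | 1.30 | 70.5% | 380 | 7.5% |

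**4. Pairing only (one lesion per patient).**

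| rho | VF | Power with a paired analysis | False non-inferiority if ignored |
|---|---|---|---|
| 0.05 | 0.95 | 82% | 4.6% |
| 0.1 | 0.90 | 84% | 4.1% |
| 0.2 | 0.80 | 87% | 3.3% |

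**5. Both together.**

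- Mean 1.2, ICC 0.1, rho 0.05: VF = 1 + 0.033 − 0.05 = 0.983, slightly conservative.
- All patients with 2 lesions, ICC 0.1, rho 0.1: VF = 1.00, exact cancellation.
- All with 2 lesions, ICC 0.3, rho 0.05: VF = 1.25, power 72.0%, risk 7.1%.

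The factor falls on both sides of 1.

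**6. The test that 12.2 names.** The risks above suppose a one-sided 0.05 non-inferiority limit, which 12.2 does not spell out. For the two-sided Chi-square test with 1.5% recurrence in both groups, the exact false-positive rate is 4.6% for independent lesions. Simulated with clustering only, it is about 5% at mean 1.2 and ICC 0.1, and about 8% at 2 and 0.3.

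**7. Number of events.** 293 × 0.015 = 4.4 expected recurrences per group, so the normal-approximation figures in steps 1 to 5 are indicative only.

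**The case against.** **The applicability qualifier could cover McNemar.** Section 12.2 runs Chi-square tests only where they apply, and in a study named as matched pairs that could mean McNemar's test. This is a fair reading, but it handles the pairs and leaves several lesions per patient untouched.

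**The ceiling of 320 subjects for 293 lesions suggests one lesion each.** It permits that but does not establish it. The ceiling is an upper limit, and 12.2 lets the lesion count determine how many patients are enrolled.

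**The effect may be small.** This stands in part. At about 1.2 lesions per patient and a modest correlation, the named test stays close to 5%. The 7.5% and 8% figures need every patient to contribute two lesions, which is about 147 patients per group (293/2). However, a reader might infer that the whole problem vanishes when most patients have one lesion. It does not: that removes only the clustering part. A pair correlation of 0.2 with one lesion each still gives 3.3% instead of 5%. The pairing part is small only if the pair correlation is small. That is plausible at a 1.5% event rate: assumed risk strata of 1% and 3.5% in an 80:20 mix induce a correlation of about 0.007.

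**One patient in both groups is speculative.** Nothing in 7.6 bars it, but the synopsis total of 640 patients equals 320 + 320, which counts the groups as different people. It is a reason to keep one patient identifier across groups, and no more.

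**Conclusion.** The omission is real: the design matches lesions and allows several per patient, and the named analysis accounts for neither. The planned standard errors are correct only if the two correlations are zero or offset each other.

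Two stronger readings are tempting. One is that the plan inflates the risk of wrongly claiming non-inferiority; the other is that 293 lesions are too few. The documents support neither as a general statement. Clustering pushes that way and pairing pushes the other way, and nothing in the protocol fixes their sizes. In the assumed settings shown, the variance factor runs from 0.80 (pairing only) to 1.30 (clustering only).

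The clustering part is small if most patients have one lesion. The pairing part does not depend on lesions per patient. The point should be corrected before outcome data are reviewed, but it does not invalidate the design. Whether one-sided 0.05 fits with two-sided testing is a separate matter.

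**What to change.** **Change to section 12.2.**

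1. Replace the plain lesion-level Chi-square tests with an eBx minus Mohs comparison whose variance accounts for both matched pair and patient. One option is a two-way cluster-robust variance, with a single patient identifier across both groups.
2. For recurrence, check by simulation before data review that the chosen confidence limit holds its error rate at the 2.5% margin. With about 4.4 events per group this cannot be assumed: the two-way variance has been checked here only as a test of no difference, not as a non-inferiority limit.
3. Add a matched analysis using one lesion per patient, as supportive only. If collection stops at 293 lesions and patients average 1.2, about 293/1.2 = 244 pairs remain, with power Φ(0.025/√(0.02955/244) − 1.645) = 73%. But 293 is a minimum in section 8.2, and up to 320 subjects per group are allowed, so up to 320 pairs and 83% power by the same formula are possible.
4. State that 80% power with 293 lesions assumes no within-patient or within-pair correlation, and report lesions per patient by group.

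**Cost.** A short rewrite of 12.2, pair and patient identifiers kept in the dataset, a simulation, and slightly more analysis work. Intervals may be wider, and power below the stated 80%.

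### The study is sized for non-inferiority with a 2.5-point margin, but the only primary test named is a two-sided Chi-square test, and no decision rule uses the margin

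*Combined protocol and SAP*

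**What the plan says.** The sample-size paragraph of section 12.2 describes a calculation made "using a 1.5% historical 3-year recurrence rate for NMSC treated with Mohs, and a 2.5% non-inferiority margin". It continues: "A total of 293 lesions for each treatment group will provide 80% power with a 0.05 alpha level of significance". It does not say whether that alpha is one-sided or two-sided, what true eBx rate was assumed, or whether the margin is absolute.

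The next paragraph of 12.2 is the whole of the analysis plan for the primary endpoint: "The primary endpoint of freedom from recurrence and the secondary endpoints will be summarized for each treatment group and Chi-square tests performed as applicable". It adds: "All tests will be 2-sided, with significance level set at 0.05".

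Two features of the data bear on the choice of test. Section 8.2 says: "Each lesion from the eBx treatment group will be matched to a lesion treated with Mohs surgery". Section 12.2 says: "There may be more than one lesion per patient that is matched to another lesion in the other treatment group".

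The margin is mentioned nowhere else. The synopsis, the objectives (7.3) and the endpoints (7.4 and 7.5) contain no non-inferiority hypothesis, no confidence interval and no success criterion.

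**The concern.** A non-inferiority study asks whether the new treatment's recurrence rate can be shown to exceed the control's by less than the margin. A two-sided Chi-square test asks whether the two rates differ at all. Failing to find a difference does not exclude one larger than 2.5 points, least of all when recurrences are this rare: at 1.5%, 293 lesions yield about 4.4 events per group (293 × 0.015).

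The protocol does not say that p > 0.05 will be read as comparable outcomes. It gives no other rule, however, so nothing prevents that reading. The level is also unsettled. The two-sided 0.05 set for all tests is not the level that reproduces 293, and the choice can change the conclusion. Finally, an ordinary Chi-square test assumes independent lesions, whereas these are matched one to one and may be clustered within patients.

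**Working it through.** **Inputs from section 12.2:** Mohs recurrence 1.5%; margin 2.5%; 293 lesions per group; 80% power; alpha 0.05. **Assumed, because not stated:** true eBx rate also 1.5%, margin in absolute percentage points, independent lesions.

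**1. Reproduce the sample size.** With the simple unpooled-variance formula for non-inferiority,

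n = (z₁₋α + z₀.₈₀)² × 2p(1 − p) / margin²

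- One-sided 0.05: (1.645 + 0.842)² × 2 × 0.015 × 0.985 / 0.025² = 6.183 × 0.02955 / 0.000625 = 292.3, so **293**. This matches the plan.
- One-sided 0.025: 7.849 × 0.02955 / 0.000625 = 371.1, so **372**. This does not match.
- A two-sided test of difference, 1.5% against 4.0%, would need **671** per group for 80% power. At 293 its power is about 46%.

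The sizing is therefore a one-sided 0.05 non-inferiority calculation. By the same formula, 293 per group gives 80.1% power at one-sided 0.05 and 70.2% at one-sided 0.025.

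**2. What a non-significant Chi-square result would mean.** Exact enumeration of two independent binomials, 293 per group, Mohs rate 1.5%, Pearson Chi-square without continuity correction:

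| True eBx rate | Chi-square non-significant |
|---|---|
| 1.5% | 95% |
| 3.0% | 77% |
| 4.0% (at the margin) | 53% |
| 5.0% (beyond the margin) | 31% |

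For comparison, a score (Farrington-Manning) non-inferiority test at a true eBx rate of 4.0% passes 4.6% of the time at one-sided 0.05 and 2.2% at one-sided 0.025.

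**3. Worked results against 4 Mohs recurrences in 293.** Upper limits are for eBx minus Mohs, in percentage points. Non-inferiority needs a limit below 2.5.

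| eBx recurrences | Difference | Chi-square p | Score limit, 90% / 95% interval | Wald limit, 90% / 95% interval |
|---|---|---|---|---|
| 5 | 0.3 | 0.74 | 2.26 / 2.73 | 2.01 / 2.33 |
| 6 | 0.7 | 0.52 | 2.71 / 3.20 | 2.44 / 2.78 |
| 11 | 2.4 | 0.067 | 4.83 / 5.39 | 4.53 / 4.94 |

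All three are non-significant by Chi-square. With 11 recurrences non-inferiority fails under every method and level. With 5 or 6 the answer depends on the method and level, neither of which the plan states. Tango's matched-pair limits, taking every recurrence as discordant, are within 0.03 points of the score limits.

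**4. Power of a margin-based analysis at 293, true rates 1.5% in both groups.**

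| Method | 90% interval | 95% interval |
|---|---|---|
| Simple formula | 80% | 70% |
| Farrington-Manning, exact | 72% | 57% |
| Tango, exact, within-pair correlation 0 | 72% | 58% |
| Tango, exact, within-pair correlation 0.1 (assumed) | 75% | 61% |

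Clustering of lesions within patients is not modelled, because the documents give neither lesions per patient nor a correlation.

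**The case against.** The strongest reply has four parts.

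- **The question can still be answered.** The margin is stated in advance and the primary endpoint will be summarized by group, so anyone can compute the difference and an interval from the counts. That is true. But the analyst would choose the interval method and level after seeing the counts, and the results with 5 and 6 recurrences show that this choice can decide the conclusion.
- **The examples depend on preferring a score interval.** With the Wald interval, which corresponds to the formula behind 293, 6 against 4 passes at 90% and 5 against 4 passes at 95%. Exact Wald power at 293 is about 82% and 70%, so using the margin need not cost power. These figures are correct. The Wald rule is, however, liberal here: at a true eBx rate of 4.0% it passes 6.9% of the time (nominal 5%) and 3.5% (nominal 2.5%). The dependence on method is a reason to fix the method in advance.
- **The 53% and 31% belong to a rule the protocol never states.** This is fair. They measure the risk of a reading that the plan leaves open; they are not operating characteristics of a stated rule.
- **The stated aims are descriptive.** Sections 6 and 7.3 speak of understanding and evaluating outcomes and promise no non-inferiority claim. That softens the tone of the aims, but 12.2 still justifies the sample size and power by a margin that the analysis never uses.

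It also stands that the one-sided level and the equal rates behind 293 are inferred from an exact match, not stated, and that pairing changes the limits very little.

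**Conclusion.** The point holds and must be fixed. The stated 80% power belongs to a non-inferiority test that the plan does not contain. The test it does name has about 46% power to detect a true difference equal to the margin, and its non-significance says little about whether the margin is met: it is non-significant 53% of the time when eBx is exactly 2.5 points worse. The level is also inconsistent. The figure of 293 fits one-sided 0.05, while non-inferiority judged by a two-sided 95% interval needs 372 by the same formula.

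These figures assume an absolute margin, a Mohs rate of 1.5% and independent lesions; the power figures for non-inferiority also assume 1.5% on eBx. The mismatch between sizing and analysis depends on none of these numbers, since it is evident from the two paragraphs of 12.2.

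**What to change.** Rewrite the analysis paragraph of 12.2 so that the primary analysis is a non-inferiority analysis:

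1. State the null hypothesis: recurrence on eBx minus recurrence on Mohs is at least 2.5 percentage points. Say that the margin is absolute.
2. Report the risk difference with a score-type interval for matched pairs (Tango). Pre-specify a version or sensitivity analysis whose variance allows for several lesions per patient.
3. Conclude non-inferiority only if the upper limit is below 2.5 points.
4. Fix the level before the groups are compared. A 90% two-sided interval corresponds to the one-sided 0.05 that reproduces 293; a 95% interval corresponds to the two-sided 0.05 stated for all tests.
5. Restate the power for the chosen method and level.
6. Keep Chi-square or Fisher tests for the secondary comparisons.

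This costs wording and a short program, with no new type of data. The real cost is candour about power: about 72% (90% interval) or 58% (95% interval) with Tango at 293 independent pairs. Clustering would lower these figures and positive within-pair correlation would raise them. Stating the lower power is enough. If the sponsor prefers to keep 80%, exact Tango power reaches 81% with 360 pairs (90% interval) and 82% with 470 pairs (95% interval). Under the cap of 320 subjects per group, that is possible only if some patients contribute more than one lesion.

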Lovett et al reported on 339 patients who were consecutively treated for histologically confirmed basal cell (71%) and squamous cell (29%) carcinoma. A retrospective study was performed to assess local recurrence. The majority of the basal cell lesions (93%) and 97% of the SCCs were on the head. Radiation therapy was the initial treatment modality in 212 patients, and 127 patients were treated with radiation therapy after the initial surgical excision failed. Tumor control was analyzed by the type of external beam radiation therapy administered. The local control for superficial x-ray ranged from 91 to 100% reported categorically by tumor size. Electron beam ranged from 70 to 75% local control. Patients were stratified into groups by the

type of radiation beam used on the treatment. Excellent to good cosmesis was seen in 97% of the patients treated with superficial X-rays and in 78% of the patients treated with electrons, 78% of the patients treated with mixed beams, and in 80% of the patients treated with megavoltage photons. The overall complication rate (complications were defined as grade 4 toxicities) for the 310 patients whose data was available was 5.5%. Of the 217 previously untreated patients, the complication rate was 3.2%.

Silva et al report on a retrospective review of radiation therapy treatment for basal cell, squamous cell, and basal-SCC from 313 patients with 334 lesions treated. The objective of this study was to assess local control and late toxicities in patients treated with radiation therapy for the treatment of cancer of the pinna of the ear. For 270 patients, radiation therapy was the primary treatment, 50 patients received radiation therapy for recurrent cancer that had not previously undergone resection, and 12 patients received radiation therapy as an adjuvant treatment.

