#### 8 METHODOLOGY

#### 8.1 Identifying the Population

The first phase of this study will be to identify patients who completed treatment with eBx or Mohs treatment approximately 3 years ago or more prior to study onset and collect history and demographic data, and eligibility and treatment planning and treatment data retrospectively from the patient records and on source worksheets to complete a matched pair cohort study comparison.

This phase will include a review of the site's patient medical records to determine if the source documentation contains the variables that are needed to determine eligibility and which will be used in the endpoint analyses. These variables include:

- Patient Age (within  $\leq 15$  year brackets)
- Pathology report for evidence of:
  - Lesion size (cm)
  - Lesion diagnosis (BCC, SCC)
- Last treatment date for each location
- Lesion location (e.g. face, extremities, neck, nose, scalp, torso)
- Toxicities at time of prospective follow-up visit

Matching will be performed according to:

- Calendar year of treatment for equivalent follow-up
- Patient age bracket [15-year brackets or less]
- Lesion diagnosis (BCC, SCC)
- Lesion size range (< 1 cm,  $\geq$ 1 and <2 cm,  $\geq$ 2 and <3 cm,  $\geq$ 3 and  $\leq$ 4 cm)
- Location according to the methodology below:
  - o Scalp
  - Face (includes neck)
  - o Nose
  - o Ear
  - o Torso
  - Upper extremities (Arms, hands, fingers)
  - Legs (Thighs, lower leg, feet, toes)

Data Collected Prospectively:

- Cosmesis rating by physician
- Cosmesis rating by the patient
- Recurrence of cancer
- Chronic toxicities
- Patient reported outcomes (PRO) survey

Patients who return for long-term follow-up will be required to provide informed consent for both the retrospective data and the prospective data that are collected at the time of the visit.

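### Cosmesis, toxicity and patient-reported outcomes are compared by unadjusted Chi-square tests after coarse matching, so any systematic within-band difference in age or lesion size would be read as a treatment effect

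*Combined protocol and SAP*

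**What the plan says.** Section 12.2 gives one inferential method for the secondary endpoints: "the secondary endpoints will be summarized for each treatment group and Chi-square tests performed as applicable". It adds: "All tests will be 2-sided, with significance level set at 0.05". No covariate, regression, stratified or paired analysis, or balance table is described.

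Section 8.2 states that the design cannot be randomised. Section 8.1 matches on calendar year of treatment, diagnosis, location, age ("Patient age bracket [15-year brackets or less") and size, in four bands beginning with "Lesion size range (< 1 cm" and ending at 4 cm. Section 8.2 words the age criterion more softly: "Patient age bracket [Attempt to ensure 15-year brackets or less". Under Section 8.1.1, Mohs patients who match are called consecutively, so nothing selects the closest match within a band.

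Size is taken from the pathology report in centimetres ("Lesion size (cm"). Age appears in the same variable list only by bracket, although the eligibility criterion "Greater than 40 years of age" and the demographics form in Section 12.1 imply that the actual age is known.

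**The concern.** Matching to a band leaves room for difference inside it. Two matched patients can be almost 15 years apart, and two matched lesions almost 1 cm apart. In the band from 1 to under 2 cm, that is nearly a two-fold difference in diameter and nearly four-fold in area. Under randomisation such differences would average out. Here they need not, because treatment was chosen for clinical reasons.

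The protocol treats age and size as important enough to match on. The Chi-square test uses neither beyond the band, so it credits any systematic residual difference to the treatment. Cosmesis, toxicity and patient-reported outcomes are stated eBx versus Mohs comparisons in the synopsis, and the plan contains no step that would reveal such a difference.

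**Working it through.** **Group size.** The plan's 293 lesions per group is reproduced by n = (z0.95 + z0.80)² × 2p(1−p) / margin², with p = 0.015 and margin = 0.025 from Section 12.2: (1.645 + 0.842)² × 2 × 0.015 × 0.985 / 0.025² = 292.3, rounded up to 293. This uses a one-sided 0.05 level, which is a separate matter. Here 293 serves only as the group size. The plan gives no figure for the secondary endpoints.

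**Assumptions, none from the documents.** There is no treatment effect and lesions are independent. The rate of good or excellent cosmesis in mid-bracket is 90% or 70%. The log-odds fall by 0.03, 0.05 or 0.07 per year of age (odds down about 3% to 7%). Ages lie within one 15-year bracket. For mean gaps of 0.5, 1 and 2.5 years, eBx ages are tilted linearly towards the older end and Mohs ages are uniform. For 5 years, the two groups are tilted in opposite directions.

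**Formula.** Let p1 and p2 be the resulting group rates and p̄ their mean. Then s0 = √(2p̄(1−p̄)/293), s1 = √((p1(1−p1) + p2(1−p2))/293), and the rejection probability is Φ((|d| − 1.96 s0)/s1) + Φ((−|d| − 1.96 s0)/s1), with d = p1 − p2.

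**One case by hand.** Take a 70% rate, slope 0.05 and a 5-year gap. The logit of 0.70 is 0.847, and each group mean lies 2.5 years from mid-bracket, so the logits are 0.847 ± 0.125. The rates are about 72.6% and 67.3%, so d is about 5.2 points. With s0 = 0.038, d/s0 is about 1.39, and the test rejects about 28% of the time.

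**All cases, over the three slopes:**

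| Mean age gap | 90% rate: false difference (points) | Rejection | 70% rate: false difference (points) | Rejection |
|---|---|---|---|---|
| 0.5 y | 0.1 to 0.3 | 5.0% to 5.2% | 0.3 to 0.7 | 5.1% to 5.4% |
| 1 y | 0.3 to 0.6 | 5.1% to 5.7% | 0.6 to 1.5 | 5.3% to 6.7% |
| 2.5 y | 0.7 to 1.6 | 5.8% to 9.4% | 1.6 to 3.7 | 7.0% to 15.7% |
| 5 y | 1.4 to 3.2 | 8.5% to 24.5% | 3.2 to 7.3 | 13.2% to 48.4% |

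Simulation of the 2.5- and 5-year cases, with sampling error and small differences in where the base rate is set, puts the upper ends at up to about 17% and 52%. A logistic model with age in years rejects about 4% to 6% of the time in those cases, which is compatible with 5%.

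**Size and age together.** Take an outcome with a 10% base rate. Gaps of 0.1 cm and 2 years, with odds ratios of 1.5 per cm and 1.2 per 10 years, give 0.7 points and 5.9% rejection. Gaps of 0.25 cm and 2 years, with odds ratios of 2 and 1.5, give 2.5 points and 16%. These inputs are also assumed.

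**Price of adjustment.** The treatment standard error grows by about 1/√(1−R²), where R² = (g²/4)/(v + g²/4), g is the mean gap and v is the average within-group variance of age. The variance is 225/12 = 18.75 for uniform ages and 225/18 = 12.5 for tilted ages.
- g = 2.5: v = 15.625, R² = 1.5625/17.1875 = 0.091, factor 1.05.
- g = 5: v = 12.5, R² = 6.25/18.75 = 0.333, factor 1.22 (up to about 1.23 in simulation).

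**The case against.** The strongest reply is that no within-band imbalance has been shown, and that is correct. Section 4 says radiation was selected where surgery was not an option. A reader might infer that eBx patients sit at the older end of each bracket, but the passage mentions neither age nor size. A reader might also take the sentence "The local control for superficial x-ray ranged from 91 to 100% reported categorically by tumor size" as evidence of a size effect on these endpoints. It concerns local control in a cited series, not cosmesis, toxicity or patient-reported outcomes.

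The high rejection rates need opposite skews in the two groups and a steep slope. At a gap of a year or less the Chi-square test is nearly unaffected. Fifteen years is also the widest bracket Section 8.1 allows, although Section 8.2 only attempts it.

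The words on applicability in Section 12.2 leave room for other tests, and the survey and case report form are separate documents, so their scales are unknown here. That permits an adjusted analysis but commits to none, and choosing one after seeing the data would weaken it.

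Finally, if patients were selected by surgical candidacy, adjusting for age and size leaves that confounding in place. This stands: the adjusted result must not be presented as free of selection bias.

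**Conclusion.** The point holds as a cheap improvement to the secondary analyses. The plan relies on coarse matching alone and then tests without adjustment, so a systematic within-band difference in age or size would pass into the treatment comparison.

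The size depends wholly on assumed gaps, slopes and base rates, with 293 independent lesions per group. It runs from negligible (a gap of a year or less) to serious (about 8% to 52% rejection at 5 years).

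Three stronger readings are not supported. The documents do not establish that the actual error rate differs from 5%, because no imbalance is shown. They do not establish that exact values of both variables are available: size in cm is listed, while age in years is inferred. Nor is adjustment free, since the standard error rises when imbalance exists.

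**What to change.** In Section 12.2, prespecify for each categorical secondary endpoint a logistic or proportional-odds regression on treatment, age at treatment in years and lesion diameter in cm. Include the other matching factors (diagnosis, location, calendar year) or the matched pair. Use standard errors that allow for matched pairs and for several lesions per patient, for example by GEE. The form of the model for the patient survey should follow its scale.

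State that age is recorded in years, not only by bracket. Tabulate age and size by treatment group for all endpoints, including the primary.

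Do not regress the primary endpoint on several covariates: at the planned 1.5% rate, 586 × 0.015 = 8.8 recurrences are expected. Keep the consecutive calling of Mohs patients in Section 8.1.1. Switching to nearest-match calling would change recruitment after visits began (first visits from August 2016; this revision is dated March 2017).

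The cost is one model per endpoint, confirmation that age in years is captured, and a larger treatment standard error if the groups differ: about 5% at a 2.5-year gap and about 23% at 5 years. The report should say that adjustment does not address selection by surgical candidacy.
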